Despite the effectiveness of positive airway pressure for treatment of obstructive sleep apnea, many patients find it uncomfortable and are unwilling to use it, with reported utilization for >4 hours per night in fewer than two-thirds of patients in most reports, with adherence generally worse in asymptomatic or mildly symptomatic patients (51). As sleep apnea in HF patients is often asymptomatic, adherence to positive airway pressure therapy is likely to be particularly problematic. In the CANPAP trial, even among patients completing the study, average nightly use of CPAP after 1 year was only 3.6 hours (42).

Oxygen as an alternative therapeutic option in sleep apnea. Despite evidence that hypoxemia plays a major role in the cardiovascular consequences of sleep apnea, there has been little research into the potential benefits of supplemental oxygen to treat this condition. Supplemental oxygen delivered by nasal cannula during sleep is very well tolerated; our preliminary experience indicates substantially greater adherence to nocturnal supplemental oxygen than to CPAP for treatment of sleep apnea in patients screened for sleep apnea in a Cardiology clinic (Section 2.7). In patients with obstructive sleep apnea, several studies have demonstrated that supplemental oxygen at 1-4 liters per minute delivered by nasal cannula improves hypoxemia but does not reduce the AHI. In one study of patients with moderate to severe obstructive sleep apnea, oxygen was delivered at 2 lpm in those with a nadir oxyhemoglobin saturation below 80% at baseline, and at 1 lpm in those with a higher nadir saturation. This was sufficient to increase the mean nadir saturation from 70% to 90%, and reduced the frequency of 4% desaturation events by 89% (52). In another study of patients with moderate to severe obstructive sleep apnea, supplemental oxygen at 3 lpm improved nocturnal oxyhemoglobin saturation but had no significant impact on other measures of sleep quality (53). In a sample of 46 patients who underwent ambulatory blood pressure monitoring, blood pressure was modestly but not significantly reduced in the group receiving supplemental oxygen compared to those receiving placebo CPAP, with an effect approximately half as large as therapeutic CPAP (54).

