At the screening visit, adherence to current medical treatment guidelines for heart failure will be assessed using a standardized checklist based on the 2009 American College of Cardiology/ American Heart Association Guideline Update for Evaluation and Management of Chronic Heart Failure in the Adult (33), and reviewed by a study

physician to ensure adherence to these guidelines. Particular attention will be paid to the use of angiotensin converting enzyme inhibitor (or angiotensin receptor blocker) and beta blocker in all patients unless contraindicated. Where adherence to these recommendations is not met, the treating physician will be contacted by a study physician to discuss the rationale for current therapeutic choices and, if appropriate, the patient will be referred to the Heart Failure Clinic for optimization of care prior to the baseline visit.

Portable Sleep Monitoring

At the Screening Visit, after written informed consent is obtained, subjects will be instructed in the use of the Embletta Gold portable monitor (Embla Systems, Inc., Broomfield, CO). This battery-operated device can store data at 200 Hz, with 125 MB of storage capacity allowing storage of data from up to 24 hours of recording. The device contains the critical sensors which are recommended by the American Academy of Sleep Medicine (AASM) as validated sensors for measuring sleep apnea (60): airflow via a nasal cannula/pressure transducer system and oronasal thermocouple; respiratory effort via thoracic and abdominal inductance plethysmography; and oxyhemoglobin saturation via finger pulse oximetry (NONIN OEM board). In addition, signals are captured for body position and a 3-lead ECG.

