Subjects will be taught how to self-apply the sensors in their own homes. Application of sensors will be demonstrated by a trained staff member. Subjects will be asked to demonstrate their understanding of sensor placement and will be provided with simple pictorial and written instructions. Subjects will be asked to apply the sensors before bedtime and remove them upon awakening. A 24-hour phone service will be available to provide assistance should questions arise once the participant is home. Patients are instructed to depress the event marker button 3 times in succession at the time of lights off, and again upon arising in the morning. They are also asked to complete a simple sleep diary, indicating bed time, rise time, and any long periods of wakefulness during the night of the study. When units are returned to the clinic site (by mail or direct drop-off), the data will be downloaded to local computers, reviewed by the Research Coordinator, and saved to a secure drive for review by a trained research polysomnography technician based at the VA Connecticut, who will score the studies and grade them for quality. Studies will be scored following AASM guidelines for standard hypopnea and apnea definitions based on respiratory effort, flow sensors and oximetry (60). Studies that do not meet minimal quality grades (4 hours of scorable record) will be repeated.

Patients who have had a recent sleep study demonstrating the presence of sleep apnea meeting criteria for inclusion in this study, but not yet treated, may proceed to randomization without repeating the portable sleep study.

Baseline (randomization) visit

Participants with at least moderate sleep apnea with a prominent central component (AHI >15, with central AHI >5) on portable sleep monitoring will proceed to the baseline study visit. Participants will be instructed to arrive between 7 and 9 AM on the day of the baseline visit, and asked to eat only a light breakfast on the day of the visit. The visit will begin with a blood draw, after which participants will proceed with the remaining baseline measurements and be instructed in use of the ambulatory blood pressure monitor.

These baseline measures will be followed by randomization to one of the three

treatment arms and training in the assigned intervention. The entire baseline visit is expected to take approximately 4 hours.

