In addition to HLSE, this intervention includes nightly treatment with nocturnal supplemental oxygen (NSO). Oxygen therapy will be initiated at 2 lpm via nasal cannula, with routine clinical follow-up using overnight oximetry to assess adequacy of this flow rate. If needed, oxygen will be increased in 1 lpm increments as needed to (1) maintain baseline saturation >90%, and (2) to reduce the frequency of 3% oxyhemoglobin desaturation events to <5 per hour (independent of baseline saturation level). As oxygen at 2 lpm via nasal cannula has been shown to reduce the number of 4% desaturations during sleep in patients with sleep apnea by 89%, we anticipate that most participants will be adequately treated at 2-4 lpm. Oxygen is provided by a stationery oxygen concentrator. Adherence with oxygen use is measured by hours of machine use over the intervention period.

Interim telephone contact

Following initiation of therapy, study staff will make telephone contact with each participant at weeks 1, 2, 4 and 8 to identify any early problems with treatment adherence and to ascertain any adverse events. In particular, sleepiness will be re-assessed using the Epworth Sleepiness Scale and [name] or [name] will contact any patient whose Epworth Sleepiness Scale score is ≥ 16 or who provides a response of 2 or 3 on the item regarding drowsy driving. At week one the Healthy Lifestyle Education will be presented to each group over the phone in conjunction with education materials set home with patient at baseline visit.

Final study visit

After 12 weeks of intervention, participants will return for a final study visit at which time all procedures performed at the baseline visit will be repeated, including phlebotomy, echocardiography, cardiopulmonary exercise testing, and questionnaire administration. Participants will be asked to complete, while wearing the assigned therapy 24-hour ambulatory blood pressure monitoring.

Following completion of study procedures, each participant will be encouraged to accept referral to a sleep specialist within the VA to discuss treatment of sleep apnea.

Statistical analysis

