This study is a randomized clinical trial with three parallel treatment groups, designed to compare the active treatment groups (CPAP and NSO) to the optimal medical management comparator (HLSE). Baseline data will be summarized using standard descriptive statistics for demographic and baseline clinical characteristics by treatment group. Based on our experience with the HeartBEAT Study, the rate of dropouts during the course of the three-month trial is expected to be low and we do not expect dropouts

to be differential with respect to treatment group assignment. The main analysis will include all subjects completing the follow-up examination. For the purposes of a sensitivity analysis, a result of “no change” will be imputed for all drop-outs, and compared to the main analysis.

The analysis for each of the primary outcome measures (LVEF and peak VO₂) will consist of a one-factor analysis of variance comparing the mean changes from baseline in LVEF (or VO₂). As we postulate similar benefits from CPAP and NSO, we will specify two contrasts: CPAP vs. HLSE and NSO vs. HLSE as our primary analyses. In a secondary analysis, we will also compare the effects of CPAP to NSO for the purpose of hypothesis generation for subsequent larger studies. This analysis is a simple analysis of variance, with data transformation or adoption of rank-based inference if approximate normality is not present. While the randomization should achieve approximate balance on potentially confounding conditions, analysis of covariance models that employ adjustments for recruitment site, age, sex, sleep apnea severity, comorbid illness, smoking and alcohol use will be fit to potentially improve the efficiency of the treatment effect estimates. Should a significant difference between treatment and comparator be identified, further exploratory analyses will assess the relation of adherence to therapy to change in outcome measures.

In order to compare the effectiveness of the assigned interventions in controlling sleep apnea over the course of the study, an additional exploratory analysis will compare the change in AHI, change in time in periodic breathing, and change in time at SpO₂ <90% between the baseline and final portable sleep monitoring studies. This analysis will utilize a one-factor analysis of variance. Further exploratory analyses will assess the relation of effectiveness of control of sleep apnea to changes in the primary outcome measures.

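### Apnea control is compared across arms with an AHI that depends partly on oximetry, so the oxygen arm's AHI could fall without any change in breathing

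*Combined protocol and SAP*

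**What the plan says.** The Statistical analysis section sets out the purpose, "In order to compare the effectiveness of the assigned interventions in controlling sleep apnea over the course of the study", and then the method: "an additional exploratory analysis will compare the change in AHI, change in time in periodic breathing", followed by change in time at SpO2 <90%. The change runs from the baseline to the final portable recording, by one-factor analysis of variance. A further exploratory analysis relates control of sleep apnea to the changes in LVEF and peak VO2.

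Three other places bear on what that AHI measures:

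- Portable Sleep Monitoring, scoring: "Studies will be scored following AASM guidelines for standard hypopnea and apnea definitions based on respiratory effort, flow sensors and oximetry". No desaturation threshold is given, and no hypopnea rule that does without oximetry.
- Portable Sleep Monitoring, equipment: airflow, thoracic and abdominal effort and oximetry. "In addition, signals are captured for body position and a 3-lead ECG". No EEG is listed.
- NSO Group: flow is raised as needed to hold baseline saturation above 90% and "to reduce the frequency of 3% oxyhemoglobin desaturation events to <5 per hour".

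The final portable recording is named only in the Statistical analysis section. The Final study visit section repeats the baseline-visit procedures, whereas portable monitoring belongs to the screening visit. That section requires assigned therapy to be worn for ambulatory blood pressure monitoring and does not say so for a sleep recording.

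**The concern.** One arm is titrated on a signal that is also an ingredient of the outcome used to judge all three arms. Without EEG, an arousal cannot confirm a hypopnea, which leaves desaturation as the only listed confirming signal. If a flow reduction must be accompanied by a desaturation to count, oxygen can remove it from the score while airflow stays as it was. CPAP lowers the AHI by acting on breathing, and HLSE acts on neither, so any distortion runs in one direction, toward oxygen. Time at SpO2 <90% is affected still more directly.

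Two exploratory results are at stake: the comparison of apnea control between oxygen and the other two arms, and the analysis linking control to LVEF and peak VO2. In the second, an oxygen patient whose saturation improved but whose breathing did not could be counted as well controlled. The background section itself allows that preventing hypoxemia might help without treating the apnea. An AHI that depends on oxygenation cannot test that distinction.

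**Working it through.** **1. Nearest stated figure.** The plan gives no power or effect size for the AHI comparison. The closest is 80% power for 0.84 SD with 34 active and 17 HLSE subjects, two-sided 5% (Sample size and power). Recomputed: 79.2% by the noncentral t and 80.7% by the normal approximation, so it reproduces. No stated figure is disputed here.

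**2. Model.** Hold breathing and apneas constant and suppose every hypopnea needs a desaturation to be scored. Let A be the baseline AHI, h the hypopnea share and H = A × h. The documents give neither h nor the baseline AHI distribution. I vary h over 30-70% and take A = 15 (the entry threshold) and A = 30 (assumed).

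**3. Using the protocol's 89%.** The background cites a study in obstructive apnea in which oxygen "reduced the frequency of 4% desaturation events by 89" per cent, and the NSO Group section applies that figure to this trial. The proportional fall in scored AHI is 0.89 × h:

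- h = 30%: 0.89 × 0.30 = 27%
- h = 50%: 0.89 × 0.50 = 45%
- h = 70%: 0.89 × 0.70 = 62%

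For oxygen in central apnea, the background reports AHI reductions typically of 40-75%. The upper part of the modeled range overlaps this.

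**4. Using only the titration target.** If the target is met, fewer than 5 desaturating hypopneas per hour remain (taking a scoring threshold of 3% or more). The fall is then at least max(0, H − 5):

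| A | h | H | Minimum fall per hour | As % of A |
|---|---|---|---|---|
| 15 | 30% | 4.5 | 0 | 0% |
| 15 | 50% | 7.5 | 2.5 | 17% |
| 15 | 70% | 10.5 | 5.5 | 37% |
| 30 | 30% | 9 | 4 | 13% |
| 30 | 50% | 15 | 10 | 33% |
| 30 | 70% | 21 | 16 | 53% |

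At A = 15 the bound is zero whenever h is one third or less (5/15).

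**5. Could it matter to the test?** Take A = 30 and h = 40%. The step 3 fall is 0.89 × 12 = 10.7 events per hour. With an assumed SD of AHI change of 10, 15 or 20, that is 1.07, 0.71 or 0.53 SD. With 34 against 17 subjects it would alone give p < 0.05 for oxygen against HLSE with probability 94%, 65% or 42%. These SDs are illustrative; the documents give none.

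**6. Under the alternative index.** If hypopneas are scored from flow and effort alone, the scoring-only fall in this model is zero. The same holds for an apnea index and for time in periodic breathing, taken as not read from oximetry.

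**The case against.** The strongest reply is that the plan never says a desaturation is mandatory. It names oximetry as one basis of the definitions and refers to a scoring manual that is not reproduced. If hypopneas may count without a desaturation, the artefact shrinks or disappears. This stands, and the conclusion has to be conditional.

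The background also reports that oxygen does not reduce the AHI in obstructive apnea, although it improves hypoxemia. If losing desaturations always emptied the AHI, a fall would be expected there. This shows the artefact is not inevitable. It does not show that it is absent here, because the scoring rule in those studies is not given.

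The 89% refers to 4% desaturations in obstructive apnea, whereas this trial selects for a central component, and the hypopnea share is assumed. Both points stand, so the percentages illustrate scale and do not estimate it.

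Time in periodic breathing is already planned, and it is a real partial safeguard. But the plan gives it no precedence over the other two measures and does not say which one defines control in the analysis against LVEF and peak VO2.

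Finally, a flow-based index is not free of arm effects. The monitor senses airflow with a nasal cannula and thermocouple, oxygen is delivered by nasal cannula, and CPAP uses a mask. This is a good reason to add such an index alongside the AHI and not to substitute it.

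**Conclusion.** The point holds in conditional form. To the extent that scoring a hypopnea requires a desaturation, and if the final recording is made on oxygen, the oxygen arm's AHI can fall through loss of scored hypopneas with breathing unchanged. The planned AHI cannot separate that from real control. Time at SpO2 <90% is an oxygenation measure in any case. The size cannot be fixed from the documents: about 27-62% under the 89% figure and a 30-70% hypopnea share, and possibly near zero at an AHI of 15 from the titration target alone.

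A reader might infer three stronger things that the documents do not support:

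- That oxygen patients lose most of their hypopneas by construction. The scoring text does not make desaturation compulsory, the titration target is a ceiling of 5 per hour and not abolition, and apneas are not exposed under this model.
- That the reported 40-75% fall in central apnea is itself an artefact. The overlap shows only that the two cannot be told apart with this index; part or all of that fall may be real.
- That the trial's main result is biased. The primary LVEF and peak VO2 tests, eligibility and sample size are untouched; both affected analyses are exploratory.

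**What to change.** Keep the AHI for eligibility and continue to report it. For the exploratory analyses in the Statistical analysis section:

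- Also score the baseline and final recordings of all three arms, blind to arm where possible, with an event index that needs no desaturation: the apnea index plus hypopneas defined from flow and effort.
- Name that index and time in periodic breathing as the measures of apnea control, both between arms and in relation to LVEF and peak VO2.
- Label the oximetry-based AHI as dependent on oxygenation, and time at SpO2 <90% as an oxygenation measure.
- State the hypopnea rule used for the AHI, including any desaturation criterion, in Portable Sleep Monitoring.
- List the final portable recording under Final study visit and state that it is made on assigned therapy.

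The cost is some rescoring by the same technician, from signals already recorded, and a few sentences of text. There are three downsides to acknowledge. The outcome index will differ from the eligibility AHI. Airflow sensing may differ between the cannula and mask arms. Participants randomized on a recent prior sleep study may have no study-monitor baseline to rescore.

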Ambulatory Blood Pressure Monitoring. Participants will be instructed in the use of an Ambulatory Blood Pressure monitor. The device consists of a blood pressure cuff that is connected by rubber tubing to a small pressure monitoring device that weighs only 9 oz and fits easily in a shirt pocket. The device will be programmed to measure BP at 20 minute intervals during the day and 30 minute intervals at night (11 PM to 7 AM) for the subsequent 24 hours. A pre-paid addressed box will be provided for mail return of the device.

Randomization. After completing testing at the baseline visit, and being instructed in the use of the ambulatory blood pressure monitor, participants will be randomly assigned in a 1:2:2 ratio to one of three treatment groups: **Healthy Lifestyle and Sleep Education** alone (HLSE); HLSE plus Continuous Positive Airway Pressure (CPAP); or HLSE plus nocturnal supplemental oxygen (NSO). Randomization will be performed using permuted blocks, stratified by recruitment site. A SAS program will be used to generate two separate lists of randomization assignments for the two strata. These lists will be

placed into a single data table in a Microsoft SQL Server 2008 database to serve as a lookup table. When a new participant record is created in the database, a trigger is fired on the SQL Server randomization data table that looks up the corresponding stratum using predominant sleep apnea type, picks the next assignment from that stratum, updates the lookup table with the Study ID randomized and the date/time of randomization. Due to the nature of the treatments, blinding of subjects to treatment arm is not possible. The ultrasonographers and physicians overseeing and scoring the echocardiograms and cardiopulmonary exercise tests will be blind to treatment assignment.

Treatment

Healthy Lifestyle and Sleep Education (HLSE Group)

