This study provides an opportunity to evaluate multiple intermediate measures that might shed light on the mechanism of benefit of CPAP or NSO. These analyses are considered exploratory in nature. As each of the secondary outcome measures is continuous, analysis of these variables will be treated in a similar fashion to the analysis of the primary study endpoints. For analysis of blood pressure, the 24-hour mean blood pressure and the ratio of mean nighttime to mean daytime blood pressure will also be analyzed.

Mean hours of use of therapy over the 3-month intervention period between CPAP and NSO groups will be compared using a one-factor analysis of variance, with appropriate modification as needed for deviation from normality. The number of adverse events and serious adverse events in each per study arm will be tabulated and categorized according to their severity, expectedness and relationship to the study intervention.

Sample size and power

Our primary goals are to establish the efficacies of CPAP and NSO compared to HLSE. Because past studies were suggestive of a more beneficial effect of CPAP or NSO compared to HLSE, we propose to randomize more subjects to the two experimental treatment groups. That is, we propose to allocate patients into CPAP, NSO or HLSE randomly according to a 2:2:1 ratio. This strategy also improves statistical power for the secondary comparisons between CPAP and NSO.

The sample size for this study was chosen to provide adequate power to detect a significant difference in LVEF between each treatment group and the control group (Aim

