The proposed sample size of 39 in each active treatment group and 20 in the HLSE group includes a 15% increase over the needed number of evaluable subjects, to allow for expected rates on non-completion of the protocol.

Reasons for stopping assigned treatment

As there is clinical equipoise with respect to the long-term benefits of treatment of sleep apnea in chronic HF, and the duration of the intervention is short at 3 months, there is no plan to discontinue assigned treatment due to therapeutic failure related to cardiac disease. However, as treatment of sleep apnea may be expected to improve sleepiness, any participant who develops unsafe levels of sleepiness that in the opinion of the PI place him or her at increased risk of motor vehicle accidents or other safety risks, will be treated for their sleep apnea off protocol. While serious adverse effects of either CPAP or supplemental oxygen are not anticipated, should any serious adverse events occur that in the opinion of the PI are treatment related, the treatment will be discontinued.

Human Subjects Potential Risks

The study procedures do not place the subjects at risk of harm or discomfort greater than those encountered in routine medical care. The vein puncture for blood drawing is

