The study treatments are generally considered quite safe. CPAP is an FDA-approved therapy for the treatment of sleep apnea. Its use can be associated with a number of minor side effects, including nasal congestion, runny nose, dry nose or mouth, skin irritation from the mask or headgear, aerophagia or discomfort from the mask or air pressure. Rarely, sinus problems may get worse while using CPAP and mild nose bleeds may occur. Polysomnography will be performed for the purpose of CPAP titration in patients randomized to this therapy. This procedure is inconvenient, as it requires an overnight stay in the Sleep Laboratory, but poses no major risks. There may be some discomfort from placement of the sensors on the scalp and face, and wearing the sensors may cause sleep disruption. Occasionally there is discomfort or redness at the site of sensor placement. Rarely (<1:100) the skin irritation may require treatment with a topical steroid. Supplemental oxygen delivered through the nose may be associated with minor side effects such as discomfort from the nasal prongs, dry nose, nasal stuffiness, mild nose bleeds or skin irritation. The use of a saline nasal spray can help prevent dryness and nosebleeds. Although oxygen at the levels prescribed in this study is not known to be harmful, oxygen can increase the risk of fire. It is possible that patients randomized to optimized medical care alone or with NSO may not be effectively treated for their sleep apnea for the 3 months of the study. Untreated sleep apnea may place subjects at increased risk of motor vehicle and other accidents; however, in a study of 1105 patients with sleep apnea randomly assigned to CPAP or sham CPAP for 6 months (the Apnea Positive Pressure Long-term Efficacy Study), we had no episodes of motor vehicle accidents due to sleepiness using safety education and monitoring procedures similar to those of present study.

Protection against risks

All study personnel will be fully trained and credentialed in Human Subjects Protections. All research data will be collected on standardized research forms with de-identified ID numbers, without personal identifiers. Any data collected from medical records will be entered onto case report forms with only study ID numbers, excluding personal

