identifiers. Only study personnel will have access to research data, which is kept either in locked cabinets, in password-protected computers in locked offices, or on secure password-protected drives located behind the VA firewall or at the Center for Clinical Investigation at Brigham & Women's Hospital. All personal data will be stored separately from de-identified research data, and will be stored in password-protected files behind the VA firewall or in locked cabinets within the VA. Blood and specimens will be stored using de-identified bar codes at the VA Boston and shipped to [name] laboratory, the VA Boston clinical lab for testing. Once the assays have been run on the samples, any leftovers will be destroyed.

Risks from cardiopulmonary exercise testing will be minimized by close physician supervision of testing, which will be performed by trained technicians in the Cardiopulmonary Exercise Laboratories at the VA Boston and VA Connecticut HCS sites, with emergency equipment readily available. Although patients will be encouraged to exercise to their symptomatic limits, if there are any signs of medical instability, the cardiologist will end the test before the symptomatic endpoint is achieved.

Phlebotomy will be performed by trained phlebotomists.

All CPAP devices will be equipped with heated humidifiers to minimize drying, and attention will be paid at set-up to identifying a best-fit mask to minimize mask discomfort and air leaks. Subjects will be contacted at weeks 1, 2, 4 and 8 to identify any early problems with treatment and to ascertain any adverse events, in particular the onset of dangerous levels of sleepiness. Participants will be extensively counseled at the baseline visit on safety measures related to excessive sleepiness. Participants randomized to NSO will be counseled on risks of fire from use of oxygen near open flames, including cigarettes.

Potential Benefits of the proposed Research to Human Subjects and Others

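### The planned safety table counts events per arm; adding the number of patients affected (n/N) by assigned arm is a cheap reporting improvement

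*Combined protocol and SAP*

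**What the plan says.** The last paragraph before the Sample size and power heading, in the Statistical analysis section, contains the one sentence on safety analysis: "The number of adverse events and serious adverse events in each per study arm will be tabulated and categorized according to their severity". It adds a split by expectedness and by relationship to the intervention. The phrase describing the arms is garbled, but what is tabulated is clearly a number of events. No section plans a count or percentage of participants with at least one event, and none names a denominator for safety. The main efficacy analysis uses completers.

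Four other statements bear on the point.

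- Arm sizes (end of Sample size and power): "The proposed sample size of 39 in each active treatment group and 20 in the HLSE group".
- Ascertainment (Interim telephone contact): "study staff will make telephone contact with each participant at weeks 1, 2, 4 and 8", in part "to identify any early problems with treatment adherence and to ascertain any adverse events". Protection against risks repeats the schedule.
- Expected side effects (Human Subjects Potential Risks), of CPAP: "Its use can be associated with a number of minor side effects, including nasal congestion, runny nose, dry nose or mouth, skin irritation", and others. A similar list is given for oxygen.
- Data held by participant: "All research data will be collected on standardized research forms with de-identified ID numbers, without personal identifiers" (Protection against risks). The Randomization paragraph says the system "updates the lookup table with the Study ID randomized and the date/time of randomization", which ties each ID to an arm.

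**The concern.** A table of event totals across arms of 39, 39 and 20 invites a comparison that the totals cannot bear. At the same rate per patient, an active arm would show almost twice as many events as HLSE. A reader can correct for that by dividing by arm size, but the result is events per patient randomised, which measures burden. The share of patients harmed is a different quantity, and the planned table does not contain it.

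The gap between the two depends on how often one patient contributes more than one event. Repeats are plausible here, given four scheduled enquiries and several minor side effects listed for each device. At stake is how usefully the trial describes harm, including for the long-term study it is meant to prepare. Nothing in the efficacy analysis depends on it.

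**Working it through.** **Inputs.** Arm sizes 39, 39 and 20, and evaluable sizes 34, 34 and 17, come from Sample size and power. The documents give no adverse-event rate and no measure of clustering within patients, so the event totals and clustering values below are assumptions.

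**Step 1: the plan's arm sizes.** 34 × 1.15 = 39.1 and 17 × 1.15 = 19.55, which round to the stated 39 and 20.

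**Step 2: raw totals.** At an equal rate r per patient, expected totals are 39r and 20r, a ratio of 39/20 = 1.95 whatever r is. At an assumed r = 0.5 they are 19.5 and 10.

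**Step 3: what a total says about patients.** Suppose E events fall among n exchangeable patients. Given the total, the expected share affected is 1 − P(a given patient has none).

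- Independent events (Poisson): P(none) = ((n − 1)/n)^E.
- Clustered events (negative binomial with shape k; smaller k means more clustering): P(none) = ∏ over j = 0 to E − 1 of ((n − 1)k + j)/(nk + j).

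Take 4 events among 20 and 8 among 39, about 0.2 events per patient in each arm (0.200 and 0.205).

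| Clustering | 4 events, n = 20: expected patients (share) | P(4 different patients) | 8 events, n = 39: expected patients (share) | P(8 different patients) |
|---|---|---|---|---|
| Poisson | 3.71 (18.5%) | 73% | 7.32 (18.8%) | 46% |
| k = 1 | 3.48 (17.4%) | 55% | 6.78 (17.4%) | 24% |
| k = 0.5 | 3.29 (16.4%) | 42% | 6.35 (16.3%) | 13% |
| k = 0.25 | 2.99 (15.0%) | 27% | 5.68 (14.6%) | 4.5% |

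For example, Poisson with n = 20: 1 − (19/20)^4 = 1 − 0.8145 = 0.1855, and 20 × 0.1855 = 3.71. All four events coming from one HLSE patient is rare: 0.01% under Poisson, 2.7% at k = 0.25.

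Two things follow. The total does not fix the number affected. But when clustering is the same in both arms, the shares within each row are close (at most 0.4 points apart), so events divided by N gives nearly the same between-arm comparison. The comparison shifts only if clustering differs. For instance, with Poisson in HLSE and k = 0.25 in CPAP, expected shares are 18.5% and 14.6% from almost equal event rates. That gap of 3.9 points comes from the assumption, not from the documents.

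**Step 4: precision of n/N.** Exact (Clopper-Pearson) 95% intervals:

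- 8/39 = 20.5%: 9.3% to 36.5%, width 27.2 points.
- 4/20 = 20.0%: 5.7% to 43.7%, width 37.9 points.
- With nobody affected, the upper limits are 9.0% (0/39) and 16.8% (0/20).

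**Step 5: effect of dropout.** The plan allows for 39 − 34 = 5 non-completers in an active arm and 20 − 17 = 3 in HLSE. If their events went unrecorded and all of them were in fact affected, 8/39 would become 13/39 = 33.3%, and 4/20 would become 7/20 = 35.0%. This is an extreme bound. It shows why incomplete follow-up should be visible beside n/N.

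**The case against.** The strongest reply is that one summary sentence says what will be tabulated, not that nothing else will be. A competent analyst may well report patients affected anyway, and the choice of unit in a descriptive table is close to preference. That is fair, and it is why the point is minor. It remains that the sentence names events and no other section supplies the patient count or a denominator.

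It can also be said that the planned split by severity, expectedness and relationship is more informative than a headline share with any event, which would weigh a runny nose the same as a severe event. This stands: there is no reason to demote that table.

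A reader might infer that counting events would distort the comparison between arms, for example by making CPAP look more harmful than it is. The documents do not support that. They give no event rate and no clustering by arm, so any such distortion would be put in by assumption. With equal clustering, Step 3 shows that events divided by N gives nearly the same comparison.

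Finally, all randomised patients is a harder denominator than it looks. No follow-up of adverse events or vital status after dropout is described, so a patient lost early would count as unaffected. This stands and is carried into the fix.

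**Conclusion.** The point holds as a minor reporting improvement. Followed literally, the plan produces event totals that need dividing by arm size and from which the number of patients affected cannot be recovered. In the assumed illustration, about 0.2 events per patient correspond to expected shares of roughly 15% to 19%, depending on clustering. The size in this trial is unknown because the documents give no event rate.

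The conclusion rests on two readings. The safety sentence is taken to mean events despite its garbled wording. Adverse-event data are taken to be held by study ID; this is inferred from the general statement about research data, since no adverse-event form is described. The documents do not support going further, to say that the planned table is wrong, that the safety comparison would be biased, or that any efficacy, power or stopping decision is affected.

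**What to change.** Keep the planned event table unchanged, and add to the Statistical analysis section, beside it, wording such as:

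*For all randomised patients, by assigned arm, we will report the number and percentage (n/N) with at least one adverse event, with at least one serious adverse event, and who died, with exact (Clopper-Pearson) 95% confidence intervals for estimation only. The number of patients with incomplete adverse-event follow-up will be shown per arm.*

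The cost is two sentences and four table rows, counted from data that appear to be held by study ID and linked to assignment. The sponsor should confirm that adverse events are recorded that way. No sample size, significance level or efficacy analysis changes.

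There are three downsides. The intervals are wide, so the table cannot support a claim of equal safety. Patients who leave early count as unaffected unless they are followed, hence the last row. And the count is only as complete as ascertainment: enquiry is stated for weeks 1, 2, 4 and 8, but the Final study visit section does not mention one at 12 weeks.
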